## 9.10. Data Capture

Data will be collected using a hard copy CRF and/or Electronic Data Capture (EDC) System for all site reported information.

Data points not collected and/or recorded will be considered deviations unless otherwise specified. Procedures used for data review, database cleaning, and issuing/resolving data queries will be included in the data management plan.

The Principal Investigator must ensure the accuracy and completeness of the recorded data and then provide his/her signature on the appropriate CRF/eCRFs. The Investigator's electronic signature for specific eCRFs will be documented in compliance with local regulations.

Visual and/or computer data review will be performed to identify possible data discrepancies. Manual and/or automatic queries will be created in the EDC system and will be issued to the site for appropriate response. The site staff will be responsible for resolving all queries in the database.

This study will be using a 21 CFR Part 11 compliant electronic data capture. All system level validation documentation is retained within the Information Systems group. See **Section 14.4**, Data Management.

## 9.11. Deviation Handling

A deviation is defined as an event where the exact instructions contained in this protocol or the applicable regulations have not been followed. Deviations are classified by occurrence (*i.e.*, sporadic vs. repeated) and seriousness (*i.e.*, major vs. minor). Major deviations may impact subject safety, alter the risk/benefit ratio, compromise the integrity of the study primary end point data. Minor deviations do **not** impact subject safety, compromise the integrity of the primary end point study data.

No changes to the protocol will be permitted. Investigators are required to obtain prior approval from the sponsor or designee and their respective IRB/EC and Regulatory Authority, if required, before initiating deviations from the protocol, except where necessary to protect the rights, safety and well-being of human subjects in an emergency. Such approval will be documented in writing and maintained in study files. The investigator must notify Neurolief and the reviewing IRB/EC of any deviation, which will be recorded in the eCRF, from the CIP when specific to the protection of the life or physical well-being of a subject in an emergency. Such notice must be given as soon as possible, but in no event later than 5 working days after the emergency has occurred. Prior approval is generally not expected in situations

 Neurolief Brain Innovation	MOOD: CLINICAL INVESTIGATION PLAN	Doc No.: CL-CIP-201 Rev: REV.3 / 09June2021 Pg. 57 of 92
--	--	--

where unforeseen circumstances are beyond the investigator's control, (e.g., subject did not attend scheduled follow-up visit); however, the event is still considered a deviation and must be recorded in the subject eCRF.

Deviations shall be reported to the sponsor regardless of whether medically justifiable, pre-approved by Neurolief, IRB/EC and Regulatory Authority, if required, or taken to protect the patient in an emergency. If these deviations affect the scientific soundness of the CIP or the rights, safety, or welfare of human subjects the IRB/EC will also be notified. All other deviations will be reported per the site's IRB/EC deviation policy. All protocol deviations will be reported in the eCRF. Non-subject specific deviations (e.g., unauthorized use of an investigational device outside the study, unauthorized use of an investigational device by a non-certified physician) must also be reported by the investigator to the sponsor in writing. Investigators must also adhere to procedures for reporting study deviations to their EC/IRB in accordance with their specific EC/IRB reporting policies and procedures.

The monitor will discuss deviations with relevant site personnel and will document them on monitoring visit reports.

Neurolief will review records of deviations and will consider the need for corrective and preventive action and further external reporting to regulatory authorities. Deviations will be summarized and included in the study report. Assessment and discussion of their potential impact / lack of impact on study results will be addressed.

If the deviation is performed without written approval from all parties, the investigator may be terminated from the study. Corrective and preventive actions and principal investigator disqualification will be included in the Clinical Study Management Plan and/or Monitoring Plan. If further escalation is needed, it may result in Corrective and Preventive Action (CAPA), suspension, or termination. If it is determined that there is investigator fraud, or strong evidence of fraud, the course of action may include, but is not limited to: potential exclusion from analyses, site closure, notification of the responsible IRB/EC of the actions to be taken, notification of key stakeholders and/or study team of the actions to be taken, notification of appropriate regulatory authority(ies) and/or restrictions on future participation in clinical studies.

## 9.12. **Subject Withdrawal or Discontinuation**

The reason for study exit, including screen failure, will be documented on the applicable CRF/eCRF and in the subject file. The Sponsor must be informed of each withdrawal case.

Once a subject has been enrolled in the study, he/she may withdraw his/her consent to participate in the study at any time without prejudice. Participation in this clinical investigation is entirely voluntary.

In the event the subject withdraws consent during the study, the date of withdrawal will be documented. Individual subjects will not be replaced.

 Neurolief Brain Innovation	MOOD: CLINICAL INVESTIGATION PLAN	Doc No.: CL-CIP-201 Rev: REV.3 / 09June2021 Pg. 58 of 92
--	--	--

The investigator may prematurely discontinue the participation of any subject in the study.

If the Investigator voluntarily removes a subject from further study participation, supporting documentation must be in place for the rationale and date of removal. The Investigator may withdraw a subject from the study at any time for the following reasons:

- Severe side effects clearly related to the study procedures.
- Presence or appearance of exclusion criteria
- Clinically significant current suicidal intent as assessed by the investigator team: a "yes" answer to Q4 or Q5 on C-SSRS questionnaire.
- Appearance of accompanying diseases rendering further participation in the study impossible
- A significant protocol deviation, as determined either by the Sponsor or the Investigator.
- Subject noncompliant with procedures
- Subject noncompliant with visits
- At the specific reasonable request of the Investigator

Attempts will be made to conduct an exit/final visit prior to a subject terminating participation in the study. The reason for early discontinuation will be documented in the source documents and eCRF. Data collected up to the point of withdrawal or premature discontinuation will be included in the data analysis, unless specifically requested not to.

### 9.13. **Subject Missed Contact / Visit**

Every attempt will be made to contact subjects that are noncompliant with study visits. If a subject does not show for a visit and cannot be contacted to collect follow-up information, he/she will be counted as a 'missed visit' for that specific schedule. Prior to counting the subject as a 'missed visit' the following will be performed:

- Repeated attempts to contact the subject via all available means. Each attempt should be clearly documented in the source documents and the response or lack thereof should be captured.
- Repeated, documented attempts to contact the subject's general practitioner or referring physician.
- If a visit cannot be arranged, obtain as much information as possible through all communication means with the subject and/or his/her treating physician.

If still unsuccessful to obtain information, attempts shall be made to contact the subject for the next scheduled visit. A subject will be considered 'lost' only after a period of two (2) weeks after the last scheduled visit for that subject. If a subject is lost, the methods used to attempt to contact the subject should be noted. At least three attempts should be made to contact the subject and/or his/her treating physician via all available routes, and a certified letter should be sent to the permanent address on file. A copy of the letter and return or delivery receipts should be retained in the subject's source document. The Sponsor should be notified and the End of Study (EOS) form should be completed.

## 10. Risks and Benefits

Risk management is performed as per ISO 14971, complete documentation is maintained on quality management file (Neurolief document # QAD-222).

### 10.1. Potential Risks

Technical characteristics and electrical output of the Relivion®DP are similar to other known external transcutaneous devices applying electrical stimulation for psychiatric purpose. Safety of the Relivion®DP has been extensively tested and confirmed through bench performance testing as well as throughout Neurolief's early clinical study. No serious device related adverse events were recorded during the early studies, and treatment was well tolerated by participants.

Current study design does not require application of electrical stimulation for exceptionally prolonged periods, or other circumstances where the use of the device has not yet been validated. Hence this protocol presents minimal risks to the subjects and adverse events are not anticipated beyond those reported for other electrical neurostimulation devices. Potential expected device side effects are summarized below. See **Section 11.2**.

No information is available for use of the Relivion®DP during pregnancy or lactation, so women who are pregnant or lactating are not eligible for inclusion in this study.

Participating in this study DB phase means that the subject has a 50% chance of receiving a sham treatment, which may lead to worsening of the subject Depression state (including suicidal intent).

The above mentioned risk is mitigated by the following: study patients continue using their prescribed antidepressant medications during the study duration and are closely followed up by the study team as to their mental state, including the continued assessment of their MDD severity on the HDRS score, weekly QIDS-SR-16 and the C-SSRS suicidality assessment. In the case of worsening depression symptoms, the study team will be able to unblind the subject arm and/or respond immediately with treatment change and if required study exit. In the case of worsening depression symptoms, a process for emergency unblinding is implemented during study conduct. In addition, subjects and family members would be instructed to contact the study doctor if symptoms get worse.

The risk for suicide is reduced by the study exclusion criteria by which subjects with a current suicidal intent or plan would not be randomized to the study (exclusion criteria #12: Past 12 months active suicidal intent or plan as defined by a "yes" answer to Q4 or Q5 on the Columbia-Suicide Severity Rating Scale, (C-SSRS) or with a history of suicide attempt in the past twelve months). In addition, at every follow up visit the suicidal intent will be re-assessed and documented by the study team. Throughout the study, an answer of "yes" to questions Q4, or Q5 would exclude the subject from the study.

There may be additional risks related to this study (other than those listed here) that are not yet known. Risks must be continuously monitored, assessed, and documented by the Investigator.

 Neurolief Brain Innovation	MOOD: CLINICAL INVESTIGATION PLAN	Doc No.: CL-CIP-201 Rev: REV.3 / 09June2021 Pg. 60 of 92
--	--	--

## 10.2. Potential Benefits

Neurolief's feasibility clinical study demonstrates a significant improvement effect of the Relivion®DP in subject's who suffers from MDD by an average reduction of 9 points on the HDRS score over the six weeks of treatment period. Moreover, 35% of the patients showed symptoms remission and 85% experienced a decrease in their HDRS score with no serious adverse effects over the six weeks of treatment period. It is anticipated that patients will experience similar effect under the setting of the current study.

Another known benefit to patients participating in such a study is the ability to learn more about their medical condition through the assessments that will be performed throughout the course of the study. Additionally, patients will be closely observed by the study staff throughout their participation in the study and therefore their treating physicians may be able to make more informed decisions in their medical care. Last, all assessments associated with the study, as well as the study device, are provided at no charge to the participants.

The information from this study may benefit other subjects with Major depression in the future.

## 10.3. Risk Control and Mitigation

The following efforts will minimize risks to subjects in the study:

- Conduct of the study following successful completion of extensive bench performance testing and careful risk analysis.
- Selection of investigators who are experienced and skilled in management of patients with MDD.
- Establishment of a training program for study staff members (investigators and coordinator) and use of tools that will ensure proper training to the subjects for home use of the device.
- Clearly defining the inclusion and exclusion criteria such that only appropriate patients are enrolled in the study.
- Close monitoring of worsening of depression symptoms and suicidal intent

## 10.4. Risk-Benefit Rationale

Assessing the risks against the potential benefits of the use of the Relivion®DP for improvement of MDD symptoms, Neurolief and the principal investigators have determined that there is a high likelihood that the expected benefit may outweigh the risk in patients fulfilling the study eligibility criteria.

## 11. Adverse Events and Device Deficiencies

Adverse event definitions used in this study are based on ISO 14155:2020 (Clinical Investigation of Medical Devices for Human Subjects -- Good Clinical Practice).

 Neurolief Brain Innovation	MOOD: CLINICAL INVESTIGATION PLAN	Doc No.: CL-CIP-201 Rev: REV.3 / 09June2021 Pg. 61 of 92
--	--	--

Adverse Events will be collected for all enrolled subjects with the point of enrolment (Visit #2 upon randomization) and end at the study termination visit (visit #6). Subjects with AEs at termination visit will be followed for 14 days or until event resolves, whichever comes first.

During the course of the study, all AEs will be collected and reported on the CRF/eCRF including:

- All AEs related to Relivion®DP device and/or procedure.
- All AEs not related to Relivion®DP device and/or procedure.
- All device deficiencies that may lead to a SAE.
- All Deaths

### 11.1. Definitions

Safety definitions are provided below. Clinical events to be considered and reported as AE or SAE include but are not limited to those listed in Section 11.2.

**Adverse Event (AE):** Any untoward medical occurrence, unintended disease or injury, or untoward clinical signs (including abnormal laboratory findings) in subjects, users or other persons, whether or not related to the investigational medical device and whether anticipated or unanticipated.

NOTE 1 This definition includes events related to the investigational medical device or the comparator.

NOTE 2 This definition includes events related to the procedures involved.

NOTE 3 For users or other persons, this definition is restricted to events related to the use of investigational medical devices or comparators.

**Adverse Device Effect (ADE):** Adverse event related to the use of an investigational medical device.

Note 1: This definition includes adverse events resulting from insufficient or inadequate instructions for use, deployment, implantation, installation, or operation, or any malfunction of the investigational medical device.

Note 2: This definition includes any event resulting from use error or from intentional misuse of the investigational medical device.

**Serious Adverse Event (SAE):** An adverse event that led to any of the following:

- death;
- a serious deterioration in the health of the subject, users, or other persons as defined by one or more of the following:
  - a life-threatening illness or injury;
  - a permanent impairment of a body structure or a body function including chronic diseases; or

 Neurolief Brain Innovation	MOOD: CLINICAL INVESTIGATION PLAN	Doc No.: CL-CIP-201 Rev: REV.3 / 09June2021 Pg. 62 of 92
--	--	--

- in-patient or prolong hospitalization; or
- medical or surgical intervention to prevent life threatening illness or injury or permanent impairment to a body structure or a body function;
- fetal distress, fetal death, a congenital abnormality or birth defect including physical or mental impairment.

Note: A planned hospitalization for pre-existing condition, or a procedure required by the clinical protocol, without a serious deterioration in health, is not considered to be a serious adverse event.

**Serious Adverse Device Effect (SADE):** Adverse device effect that has resulted in any of the consequences characteristic of a serious adverse event.

**Unanticipated (Serious) Adverse Device Effect (U(S)ADE):** Serious adverse device effect which by its nature, incidence, severity or outcome has not been identified in the current risk assessment, or any other unanticipated serious problem associated with a device that relates to the rights, safety, or welfare of subjects.

## 11.2. Relivion®DP Anticipated Adverse Events

Possible risks and adverse events that may be associated with the Relivion®DP device are based on adverse events reports of similarity devices include, but are not limited to the following:

- Unpleasant sensation during treatment
- Scalp Numbness sensation during and after treatment
- Persistent tingling sensation after the treatment ends
- Pain in the head and neck area
- Skin reaction (for example, irritation, lesion, burn) beneath the stimulation electrodes. In this case, treatment should be temporarily discontinued.
- Redness of the skin under or around the electrodes. Skin redness usually disappears within several hours after treatment.
- Sleepiness, fatigue or sleep disorders
- Sedative effect during or after treatment
- Dizziness during or after treatment
- Tension type headache after treatment

 Neurolief Brain Innovation	MOOD: CLINICAL INVESTIGATION PLAN	Doc No.: CL-CIP-201 Rev: REV.3 / 09June2021 Pg. 63 of 92
--	--	--

## 11.3. Reporting of Adverse Events

### 11.3.1. Reportable Adverse Events

The definition of AE applies to any underlying diseases, present at baseline, that exacerbate in severity post intervention. Therefore, an underlying disease that was present at the time of enrollment is not reported as an AE, but any increase in the severity of the underlying disease is to be reported as an AE.

All AEs including laboratory abnormalities that are deemed clinically significant by the investigator must be recorded in the source document and eCRF, irrespective of attribution to device or procedure. All clearly related signs, symptoms, and abnormal findings should be grouped under one diagnosis. A description of the event, including the start date, resolution date, action taken, and the outcome should be provided, along with the investigator's assessment of the severity, the seriousness and the relationship between the AE and the study device and/or procedure. If any radiological imaging or other testing are taken, which are related to the event, these will be added to the eCRF of the subject.

### 11.3.2. Hospitalizations

Any adverse event that results in inpatient hospitalization should be documented and reported as a serious adverse event unless specifically instructed otherwise in this protocol. Any condition responsible for surgery should be documented as an adverse event if the condition meets the criteria for an adverse event.

Neither the condition, hospitalization, nor surgery are reported as an adverse event under the following circumstances:

- Hospitalization for diagnostic or elective surgical procedures for a preexisting condition.
- Emergency department visits, unless meeting the SAE definition under another criterion.
- Social admission (e.g., patient has no place to sleep).
- Administrative admission (e.g., for yearly physical exam).
- Optional admission not associated with a precipitating clinical adverse event (e.g., for elective cosmetic surgery).
- Nursing home admission, admission to custodial care, or admission to a rehabilitation facility.

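### Section 11.3.2 tells sites not to report the condition behind an emergency department visit as an adverse event, which contradicts sections 11, 11.1 and 11.3.1 and allows uneven AE capture

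*Protocol*

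**What the plan says.** Protocol 11.3.2 (Hospitalizations) first makes an AE that leads to inpatient admission an SAE. It then says of surgery: "Any condition responsible for surgery should be documented as an adverse event if the condition meets the criteria for an adverse event". A list of exclusions follows under the lead-in "Neither the condition, hospitalization, nor surgery are reported as an adverse event under the following circumstances". The entries that matter here are:

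- "Hospitalization for diagnostic or elective surgical procedures for a preexisting condition".
- "Emergency department visits, unless meeting the SAE definition under another criterion".
- Optional admissions, limited to those where no clinical adverse event led to the admission.
- Admissions to a nursing home, custodial care or a rehabilitation facility, with no limit or exception of any kind.

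Other parts of section 11 say something different. The opening of section 11 states "During the course of the study, all AEs will be collected and reported on the CRF/eCRF including" and goes on to name both device-related and unrelated events. Section 11.1 defines an AE as "Any untoward medical occurrence, unintended disease or injury, or untoward clinical signs (including abnormal laboratory findings) in subjects, users or other persons", with no exclusion by place of care. Section 11.3.1 adds that "any increase in the severity of the underlying disease is to be reported as an AE".

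The safety endpoint (Protocol 5.1.7, SAP 8.4) is the incidence of AEs and SAEs, related or not. The primary safety variable (Protocol 12.9.4, SAP 11.5.6) is the cumulative incidence of device-related AEs. AE rates are compared between groups with Fisher's exact test.

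**The concern.** The lead-in in 11.3.2 covers the condition itself, and it speaks of adverse events rather than serious adverse events. As worded, it decides whether an event is reported at all, not only how serious it is. For emergency department visits the single way back into the data is to meet the SAE definition on another ground. A non-serious event that takes a subject to an emergency department without admission would then not be recorded, although the same event handled by telephone or in clinic would be.

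The events at risk are those for which a subject sought urgent care. An event that is never entered as an AE also misses the later steps: sponsor reporting under Table 2, narrative and adjudication under 11.3.7, and the AE summaries that go to the data monitoring committee under 14.1. If some sites follow 11.3.2 and others follow 11.3.1, AE rates will also vary by site for reasons unrelated to the device.

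**Working it through.** The plan states no figure on this point, so the check is a comparison of texts followed by one bound.

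**Step 1. Does the wording reach the condition, or only the visit?** The lead-in names condition, hospitalization and surgery separately. On its terms the condition is excluded as well as the visit.

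**Step 2. Is the emergency department entry limited by its context?**

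| Entry in 11.3.2 | Limit |
|---|---|
| Hospitalization for a diagnostic or elective surgical procedure | preexisting condition only |
| Emergency department visit | none, except that SAEs on another criterion stay in |
| Optional admission | only if no clinical AE led to it |
| Nursing home, custodial care, rehabilitation | none |

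Two neighbouring entries carry a limit that keeps new events in the data; the emergency department and facility entries do not. The section also has a sentence keeping a condition behind surgery as an AE when it meets the definition, and no counterpart for emergency visits.

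**Step 3. Does the SAE exception rescue these events?** Under 11.1 the hospitalization criterion needs in-patient or prolonged admission. A visit that ends in discharge does not meet it. A non-serious event therefore stays excluded under 11.3.2.

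**Step 4. What do the other sections require for the same event?** Section 11 requires every AE to be collected. Section 11.1 would count the event, and it points to the list in 11.2, which includes skin burn and dizziness. Section 11.3.1 requires recording in source and eCRF. Its clinical-significance qualifier may apply to all AEs or only to laboratory findings, but it is not tied to where the subject was treated. The two sets of instructions conflict.

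**Step 5. Is there a rule of precedence?** None was found in the protocol. SAP section 1 lets the SAP override the protocol where they differ, but the conflict lies within the protocol, and the SAP text available does not address AE reporting.

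**Step 6. Bound per affected subject.** Inputs: 124 planned randomised subjects aged 22-70, allocated 1:1 (Protocol 12.4 and 12.6).

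- Planned arm size: 124 / 2 = 62.
- Largest change in one arm's incidence per affected subject: 1 / 62 = 0.016, or 1.6 percentage points.

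Incidence counts subjects, so the change is zero if the subject already has another counted AE. For the primary safety variable, the other event would have to be device-related. The SAP analyses safety in the ITT set, so the realised denominator may differ somewhat from 62. The number of affected subjects cannot be derived, because no emergency visit rate is given.

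**The case against.** A reader might infer that these events are removed from the AE data and that acute worsening of depression is kept from the data monitoring committee. The documents do not support that, for four reasons.

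- A site that follows section 11 or 11.3.1 would still record the events.
- Obvious examples are covered by specific text elsewhere. Burn and dizziness are on the 11.2 list that 11.1 says is to be reported, and Table 2 requires adverse device effects to reach the sponsor within 24 hours. Worsening depression is an AE under 11.3.1. A C-SSRS answer of yes to question 4 or 5, once assessed by the principal investigator, is reported as an AE under 9.9. Worsening is also followed by HDRS, weekly QIDS-SR-16 and C-SSRS (10.1).
- The setting favours a harmless intent. The section concerns hospitalization, and the words about another criterion belong to a test of seriousness. The author probably meant only that an emergency visit does not by itself make an event serious.
- Section 14.2.2 already has monitors compare study data with medical records and look for possible AEs.

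All four points stand, and they rule out any claim of certain loss. They do not remove the defect. The likely intent is not what the sentence says, and a site could reasonably treat 11.3.2 as the specific exception to the general rule.

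Timing also matters. The SAP was signed on 29 May 2024, describes the interim analysis in the past tense (2.2.1) and already reports that only two subjects were under 22 (10.4). Recruitment appears late or finished, so rewording alone would change little.

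**Conclusion.** The point holds as an internal contradiction with a possible effect on the safety data. Section 11.3.2, read literally, excludes non-serious conditions seen in an emergency department, and conditions behind facility admissions, from AE reporting. Sections 11, 11.1 and 11.3.1 include them, and no text settles the matter. Capture may therefore differ between sites, and both overall and device-related AE incidence may be understated.

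The total effect cannot be estimated from the documents. The 1.6 points per affected subject is a maximum, resting on the planned 62 per arm and on that subject having no other counted AE. Acute events managed outside an emergency department or the listed facilities are not touched, and no efficacy result is affected. The wording should be corrected because it bears on the trial's safety endpoint and the remedy is cheap.

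**What to change.** Reconcile 11.3.2 with 11, 11.1 and 11.3.1. The listed circumstances should be said neither to make an event serious nor to be an AE on their own, with a further statement that any underlying condition meeting the 11.1 definition is still reported as an AE. A short amendment or a clarification letter to sites would do.

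The more useful step at this stage is retrospective. Before database lock, check source documents for emergency department visits and for nursing-home, custodial and rehabilitation admissions, and enter any AE that was missed. Apply the check to both arms and all sites, without reference to treatment assignment. If the database can no longer be changed, state the 11.3.2 rule in the clinical study report as a limitation of the AE incidence.

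The cost is one or two sentences, a limited source check within monitoring that is already planned, and slightly higher reported AE counts.
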